## Implementation framework: EPIS model.

The implementation approach is anchored in four stages of the EPIS conceptual model: Exploration, adoption/Preparation,

Implementation, and Sustainment. The strong evidence for SEEK's effectiveness has been underscored by its listing on the websites of the CDC, AHRQ, AAP, and by the California Clearinghouse for Evidence-Based Interventions in Child Welfare. Early adopters are increasingly implementing SEEK in primary care settings, including in Sweden. Four of the 5 healthcare systems in this proposal have implemented SEEK in some of their practices. However, practices within these systems operate independently of one another, and there should not be contamination among them. Each practice has its own lead physician, PCPs and administrative staff and several have integrated behavioral health. Given that early adopters are estimated to be 10% of those eligible and that medical innovations can take 17 years to be adopted, it is unlikely that SEEK's potential public health benefit will be realized without better methods for scaling up.

**Design.** The proposed implementation study is the first involving SEEK. We selected a rigorous Hybrid Type III design which is an approach to examine implementation outcomes while also examining SEEK's effectiveness in preventing CM, measured by EHR indicators. Type III designs are facilitated by good EHR systems due to the low cost of data routinely gathered for clinical, services, and financial purposes. This allows more resources to address the implementation outcomes of SEEK strategies in routine practice settings. In the past 4 years, over 80 papers reported use of hybrid designs. Practices will be randomized to one of the two training strategies (IND vs. MOC). Practices, however, will be able to select the facilitation strategy (SEEKonline or Traditional) as we are not able to require this of participants. The design accounts for heterogeneity in geography, size of healthcare systems, type of primary care (pediatric and family medicine), and presence of integrated behavioral health (see strong support letters from healthcare systems in Texas, Ohio, Utah, Wisconsin and North Carolina). As shown in Figure 2, professionals, office staff and parents are

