nested within practices which are nested within the 5 healthcare systems. The participating systems will be randomized to one of two start times - 9 or 16 months from project start date, beginning with one pediatric and one family medicine system (cohort 1). Staggering the start time addresses the capacity limitations of the training and research staff.

**Sample.** We will offer SEEK to the 5 healthcare systems. Inclusionary criteria are: 1) practices not already implementing SEEK, 2) practices providing primary care to children, and 3) agreement to participate. The systems have indicated a general commitment to this project; they include 59 practices with 306 PCPs. Our recruitment efforts in SEEK II were very successful with 75% (18/24) of practices agreeing to participate, including all the PCPs in those practices. We plan to study 13 pediatric and 35 family medicine practices. If more practices are interested, we will select the first 48 choosing to participate. In the unlikely event that fewer than 48 are interested, we will approach other healthcare systems. In addition to 5 system leaders, we will recruit 5 groups of participants: 1) all 48 practice leaders, 2) 275 PCPs, 3) 16 behavioral health professionals, 4) 96 ancillary staff, and 5) 288 parents (6 per practice). These estimates are based on current staffing. Smaller subsamples will be purposively selected for qualitative interviews according to practice type, training strategy and presence of integrated behavioral health.

We will also request limited consent from practice leaders and PCPs who opt out to briefly probe their decision. We will ascertain aggregated ICD-10CM-related diagnoses on all children 0-5 attending the practices (N~90,000). Based on our experience, we anticipate 60% of practice leaders and PCPs will be female as will be most of the other participants. Different regions provide diversity in terms of urban, suburban and rural locations, and racial/ethnic diversity (e.g., 2 systems serve a predominantly Latino population). Three systems have integrated behavioral health professionals. These contextual factors will be considered in all analyses.

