### **Procedures**

**Pre-implementation Phase** (5 months). Recruitment will begin and we will identify a physician "champion" and an office staff member to lead implementation in each practice. Practices will choose by month 4 SEEKonline or the Traditional paper and pencil approach. To ease introduction of the SEEK model, we will address logistical issues such as for which checkups parents will complete the SEEK PQ and documentation in the EHR. SEEK Parent Handouts will be customized with information on local resources and PCPs will complete the SEEK Primary Care Provider Questionnaire (PCPQ) prior to the SEEK training.

**Implementation Phase.** In month 5, practices in cohort 1 will be randomized to one of the two SEEK training strategies (MOC or IND), stratified by practice type (pediatric or family medicine). At the end of training in month 8, PCPs will evaluate it. After the training, PCPs will be asked to participate in 3 webinars

every 4 months to discuss implementation and clinical issues. By month 8, interested practices will have SEEKonline connected to their EHR, ensuring interoperability. In month 9, the SEEK intervention will begin in cohort 1. Practice leaders, PCPs, behavioral health professionals and office staff will be asked to complete the online SEEK Adoption Survey, regardless of full participation. Parents also will begin completing surveys. Purposive subsamples from each group will be selected for 30-minute phone qualitative interviews. The process for cohort 2 will begin in month 11 and the SEEK intervention will start in month 16. Procedures are detailed under Human Subjects for addressing concerns of possible child abuse or neglect.

**Sustainment Phase.** Participants will be assessed at 12, 21 and 33 months post baseline regarding their thinking, feeling, behavior and experiences (see Table 3) to help inform understanding of SEEK's implementation and sustainment. At months 41 and 48, the observation period will end for cohorts 1 and 2. Final surveys and phone interviews will assess participants' thoughts and plans about continued use of SEEK. Following the grant period, practices that wish to continue utilizing the implementation strategies will be guided through the process of establishing real-world, not-grant funded contracting.

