## **Data Analysis Plan**

**General Considerations.** Standard statistical methods for calculating point estimates, confidence intervals, and p-values require the assumption of independence. However, due to participants being clustered within healthcare systems and within practices, this assumption cannot be made. To account for the lack of independence among multiple measures within the same system or practice, we will use random effects (i.e., hierarchical) models. In these models, we will include a random effect for system and for practice. In analyses involving multiple measures from the same person, we will include a random effect for each one. These models can be fitted using SAS Proc GLIMMIX, which fits models for both quantitative and binary outcomes. There will be diverse analyses based on the data. Below we highlight the main analyses for each Aim. The qualitative data (see below) will inform the models through processes of convergence (i.e., triangulation) and expansion (i.e., explanation of unexpected findings from analyses of quantitative data).

Sex as a biological variable will be considered across multiple levels of analyses. At the PCP, parent, and child levels of analyses, there is the potential for variation in implementation outcomes related to sex. Analyses will include a test for sex differences; when differences are noted, additional analyses will examine the influence of additional contextual factors on these outcomes.

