**Aim 1. Compare alternative approaches to implementation of SEEK with respect to clinical and implementation outcomes.** To address aim 1a, we will compare practices randomized to MOC to practices randomized to IND with respect to clinical and implementation outcomes. These include perceptions of the training from the PCPs' evaluations, scales from the SEEK PCPQ (e.g., Competence in addressing problems) and the PCP Survey (e.g., Ease of Delivery. We will also compare the groups with respect to rates of screening and parents' receipt of services and satisfaction with the PCP. For quantitative outcomes, statistical inference will be based on linear regression models; for binary outcomes, inference will be based on logistic regression models, accounting for repeated measures within PCP and system. For example, for PCPs reported Competence we will fit this model:  $E(\text{Competence}_{ijkl}) = \beta_0 + s_i + p_j + i_k + \beta_1(\text{POST}) + \beta_2(\text{POST})(\text{MOC-4})$  where Competenceijkl stands for the competence score measured at the lth time point (l=1 or 2 for baseline or follow-up respectively) of the kth PCP in the jth practice of the ith system, and  $s_i$ ,  $p_j$ ,  $i_k$  are random effects for system, practice and PCP respectively; POST=1 if it is a post-training measure and 0 otherwise, MOC = 1 if the PCP was trained using MOC and 0 if IND, and  $\beta$ 's are parameters to be estimated. Note this model assumes that the mean baseline scores are the same in both groups, as recommended for randomized studies. This model can be fitted using restricted maximum likelihood. To avoid possible biases due to selective attrition from the training, the primary analysis will follow the "intention to treat" principle including all those randomized. Secondary analyses will be based on groups defined by training received. To address Aim 1b we will compare practices who choose SEEK-online to practices who choose the traditional approach using the same statistical methods as described for Aim 1a. Outcomes of interest will include staff satisfaction, costs, rates of screening, receipt of services, and parental satisfaction.

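### Aim 1b compares practices that chose SEEKonline or Traditional with the methods of the randomised Aim 1a comparison, and no practice characteristic is named as an adjustment term

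*Combined protocol and SAP*

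**What the plan says.** **Assignment.** Training (MOC or IND) is randomised by practice, stratified by practice type. Delivery mode is not randomised. Under Procedures, Pre-implementation Phase: "Practices will choose by month 4 SEEKonline or the Traditional paper and pencil approach". Randomisation to training follows in month 5.

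**Analysis.** For Aim 1b the Data Analysis Plan will "compare practices who choose SEEK-online to practices who choose the traditional approach using the same statistical methods as described for Aim 1a". The outcomes listed are staff satisfaction, costs, screening rates, receipt of services and parental satisfaction. The only equation in the Aim 1 text is introduced as an illustration: "For example, for PCPs reported Competence we will fit this model". It contains POST, POST by MOC, and random effects for system, practice and PCP. It has no group main effect, and the plan gives the reason: "this model assumes that the mean baseline scores are the same in both groups, as recommended for randomized studies". General Considerations adds, for clustered data, that "we will include a random effect for system and for practice".

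**Context.** The Design paragraph says the design "accounts for heterogeneity in geography, size of healthcare systems, type of primary care (pediatric and family medicine), and presence of integrated behavioral health". The Sample paragraph, after listing regional, demographic and behavioral health differences, says: "These contextual factors will be considered in all analyses". Study Limitations states that randomising delivery mode was considered and not done. Aim 2 names practice characteristics as regression predictors, but for adoption and SIC outcomes and not for Aim 1b.

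**Timing of measures (Table 3).** Screening rate and receipt of services are marked at baseline. Costs (COINS) start at the first follow-up. The office staff and parent surveys start in the Training column, by month 9 for cohort 1, which is the month SEEK begins there. For cohort 2 that column reads month 10, before the cohort's process starts in month 11, so its timing cannot be relied on.

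**The concern.** Randomisation is what lets Aim 1a compare arms without covariates. When practices select their own delivery mode, that protection is absent. A practice's type, size or behavioral health staffing may affect both whether it takes up SEEKonline and how its staff, parents and costs look later. SEEKonline use is constant within a practice, so a practice random effect cannot separate the software from the kind of practice that chose it. A system random effect removes part of a difference between systems and none of a difference within them.

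Costs have no earlier value to adjust for. Staff and parent satisfaction have at best a measurement around SEEK start. For these outcomes, measured practice characteristics are the main available control, and the Aim 1b method names none.

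Aim 1 H2, and the SEEKonline part of H3, are worded as consequences of using SEEKonline. A practice-level difference could be reported as support for them.

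**Working it through.** **1. Reproduce the plan's figure.** Table 4 gives 24 vs 72 staff for Aim 1b, 80% power and a detectable effect of 0.82 SD. Sample Size Considerations gives a two-sided 0.05 test and 1.5-fold variance inflation.

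- SE = sqrt(1.5 × (1/24 + 1/72)) = 0.289 SD
- Normal approximation: (1.960 + 0.842) × 0.289 = 0.81
- t-test version: 0.817 (variance × 1.5) or 0.822 (n divided by 1.5)

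The stated 0.82 reproduces. It covers random error only.

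**2. Effect of a residual gap, with no true SEEKonline effect.** The gap sizes are assumptions and mean what remains after the planned random effects. Rejection = P(|Z + gap/SE| > 1.96). For costs I take one value per practice and the same 25/75 split: SE = sqrt(1/12 + 1/36) = 0.333 SD.

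| Outcome | Gap (SD) | Gap/SE | Declared significant |
|---|---|---|---|
| Staff | 0.2 | 0.69 | 11% |
| Staff | 0.3 | 1.04 | 18% |
| Staff | 0.5 | 1.73 | 41% |
| Costs | 0.3 | 0.90 | 15% |

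**3. If the confounder differs only between systems.** I simulated five systems with practice type and behavioral health constant within each, a random system effect and a 0.30 SD gap (1,500 replicates). The system effect absorbs part of the gap.

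- Staff (2 per practice): estimate 0.17 SD, rejection 10.5%
- Parents (6 per practice): estimate 0.11 SD, rejection 11.5%
- With the practice covariates added: rejection 5.3% for both

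**4. Why size could matter for costs.** By Table 1 and the Training section, each PCP spends 2.5 + 3 = 5.5 hours under IND and 2.5 + 4 + 3 = 9.5 hours under MOC, if every session is attended. The mean is 275/48 = 5.7 PCPs per practice. One more PCP adds those hours whichever delivery mode is chosen. If larger practices favour one mode, the cost contrast picks this up. The documents do not say whether they do.

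**5. Equal-baseline constraint, if carried over to screening rate or receipt of services.** The share of a persisting baseline gap that reaches the estimate is (1 − ICC)/(m × ICC + 1 − ICC), with m = 90,000/48 = 1,875 children per practice and ICC assumed.

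- ICC 0.02: 0.98/38.48 = 2.5%
- ICC 0.10: 0.90/188.4 = 0.5%

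Studies' Findings reports screening below 5% of visits before SEEK. On a 5-point gap the bias is then at most 0.13 points. The share would reach 20-70% only if a single rate per practice per period were analysed (between-period correlation 0.8 to 0.3, assumed).

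**6. Precision cost of adjustment.** If the covariates explain a share R² of the choice (assumed), the SE grows by 1/sqrt(1 − R²).

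- R² = 0.1: 1.054, so 0.82 becomes 0.86 SD
- R² = 0.3: 1.195, so 0.82 becomes 0.98 SD

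**The case against.** The plan can be read more generously. The statement that "These contextual factors will be considered in all analyses" covers Aim 1b by its terms, and the Data Analysis Plan says that it highlights only the main analyses. The one equation is an example for Competence, which is not among the outcomes listed for Aim 1b. The lack of randomisation is disclosed, with a reason. The documents also describe practice type and behavioral health largely by system: the first cohort is one pediatric and one family medicine system, and three systems have behavioral health professionals. The planned system random effect would then already remove part of such a difference. Fixed system effects would absorb those two covariates altogether, leaving practice size as the main addition. Finally, nothing in the documents links any trait to choosing SEEKonline.

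Much of this stands. A reader might infer that the plan ignores practice characteristics or hides the self-selection; the Design, Sample and Study Limitations text shows otherwise. A reader might also infer that the equal-baseline constraint seriously biases Aim 1b. The documents do not apply that equation to any Aim 1b outcome, three of the five outcomes have no clear pre-SEEK value, and step 5 finds little bias for the other two unless single practice rates are analysed.

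What remains is narrower. The intention to consider context names no covariate and no method for Aim 1b, while the stated method is that of a randomised comparison.

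**Conclusion.** The point holds as a minor one. A self-selected comparison is assigned the analysis of a randomised one, and the promise to consider contextual factors is not turned into named terms. With assumed residual gaps of 0.2 to 0.5 SD and no true effect, the staff comparison would be declared significant in 11% to 41% of trials instead of 5%. Costs give 15% at 0.3 SD. A 0.30 SD difference that lies only between systems gives about 10-12%.

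These figures rest on the plan's 25/75 split and 1.5-fold inflation (for costs, one value per practice) and on gap sizes the documents do not supply. They show sensitivity and do not predict a spurious result. The finding does not reach the randomised MOC vs IND comparison or the main design.

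**What to change.** In the Aim 1b text:

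- Pre-specify adjustment of every outcome for practice type, number of PCPs and integrated behavioral health, keeping the system and practice random effects. Practice type is already the randomisation stratum; the other two are on the Demographics Form. Study Limitations says that numbers preclude a quantitative assessment of behavioral health, but an adjustment term need not have its own effect estimated precisely.
- State in advance what happens if practice type or behavioral health is constant within the five systems, for example system as a fixed effect with practice size retained.
- Treat training arm as optional and for precision only. It is randomised after the choice and is not a confounder.
- For screening rate and receipt of services, include a SEEKonline main effect instead of assuming equal baselines.
- Report H2 and the SEEKonline part of H3 as observational associations, and say that adjustment reduces measured confounding only. A trait that is not measured stays in the estimate.

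The cost is wording and no new data. The standard error would be about 5-20% larger if the covariates explain 10-30% of the choice (assumed), which takes the staff detectable effect from 0.82 to about 0.86-0.98 SD. At a 25/75 split only about 12 practices use SEEKonline, so the covariate set must stay short.

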**Aim 2. Examine variations in SEEK's implementation process and impacts and understand associated barriers and facilitators in pediatric and family medicine practices.** We will determine the proportion of practices that agree to adopt SEEK. We will then quantitatively assess the relationship between practice characteristics (e.g., demographics, EBP attitudes) and willingness to adopt SEEK. The most important independent predictors will be determined using multivariable logistic regression models. Among those that do adopt SEEK, we will assess their degree of completeness, speed, and quality of implementation using the SIC. Completeness will be summarized using the final stage attained (0-8). Speed will be summarized by the duration in each stage, and quality by the proportion of activities performed at each stage, and overall. The distribution of these variables will be determined, overall and separately, based on the type of

practice. The distribution of time to achieve each phase will be estimated using the Kaplan-Meier approach. Barriers and facilitators to implementing SEEK will be probed quantitatively and qualitatively (see below). Among practices adopting SEEK, we will examine the association between practice characteristics and measures of completeness, speed, and quality of implementation from the SIC. We will examine relationships between practice characteristics and implementation by comparing the distribution of SIC scores in groups defined by practice characteristics. Finally, the most important predictors of degree of implementation will be determined using multivariable regression models with practice characteristics as predictors and SIC measures as outcomes. In addition to studying implementation at the practice level, we will analyze the relationship between PCP level measures of implementation (e.g., screening rates) and PCP characteristics, facilitators and barriers. These models will account for clustering of PCPs within practices, as described above.

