**Aim 3. Examine the effectiveness of SEEK in reducing CM.** As in our previous studies, we will identify CM-related diagnoses, now via EHRs. We will review the EHR for each child (0-5) in each practice for two years prior to implementing SEEK and during implementation. The presence of CM-related ICD-10 codes will be recorded. The proportion of children with CM diagnoses before and during SEEK will be compared at each practice. Formal inference regarding the best estimate and statistical significance of pre-post differences will be based on a binary regression model with a random effect for site, similarly to Aim 1.

**Sample Size Considerations.** Our projected sample sizes (numbers of practices, professionals within each practice, and children in the practices) should provide good precision to estimate parameters and ample power to detect moderate associations. Table 4 below shows the detectable effect sizes for various comparisons, based on performing 2-sided .05-level tests and incorporate a 1.5-fold increase in variance and sample size to account for potential loss of power due to clustering of observations within practices and systems. In general, the detectable effect sizes are moderate, at plausible levels. We observed effect sizes of about 1.0 regarding Competence and Comfort in SEEK II. For Aim 2, assuming 90% of practices provide organizational information, we will estimate the rate of adoption of SEEK accurately,  $\pm$  15 percentage points.

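### Aim 2 will name the most important predictors of adoption from about 10 to 13 non-adopting practices, so false or strongly exaggerated predictors are likely unless the candidate set is very small

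*Combined protocol and SAP*

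**What the plan says.** The Aim 2 paragraph of the Data Analysis Plan first estimates the proportion of practices adopting SEEK. It then relates practice characteristics to willingness to adopt, giving demographics and attitudes to evidence-based practice as examples. It concludes: "The most important independent predictors will be determined using multivariable logistic regression models".

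The figures that fix the size of this analysis are elsewhere:

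- **Frame.** The Sample paragraph says of the five systems that "they include 59 practices with 306 PCPs".
- **Target.** "We plan to study 13 pediatric and 35 family medicine practices", which makes 48. It adds: "If more practices are interested, we will select the first 48 choosing to participate", and "In the unlikely event that fewer than 48 are interested, we will approach other healthcare systems".
- **Uptake.** The only rate given is from the earlier trial, "with 75% (18/24) of practices agreeing to participate".
- **Data.** Sample Size Considerations gives the precision of the adoption rate "assuming 90% of practices provide organizational information". Table 4 puts that precision at plus or minus 15 percentage points.
- **Candidates.** Under Organizational Assessment, practice leaders and PCPs who opt out are asked for the adoption survey and four measures: a demographics form, the EBPAS (four domains), the ILS (four subscales) and the ICS.

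The plan gives no list or number of candidate predictors for this model, and no selection rule, penalisation, internal validation, multiplicity control or exploratory label. No sample-size statement covers the model.

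**The concern.** The information in a logistic model is limited by the smaller outcome class, here the practices that decline. The plan sizes only the overall adoption proportion and then commits to identifying and ordering independent predictors. With very few non-adopters and an open candidate list, two things go wrong together. Testing many characteristics without adjustment makes at least one chance finding likely. And because standard errors are large, whatever reaches significance must carry a large odds ratio, true or not.

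What drives adoption is part of the question in Aim 2, and the results are meant to guide later dissemination. A spurious predictor with an impressive odds ratio could misdirect that work.

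**Working it through.** **The plan's own Aim 2 figure.** Half-width = 1.96 × √(DE × p(1−p)/n), with n = 0.9 × 59 = 53 and the plan's 1.5-fold variance inflation as DE. At p = 0.75: 1.96 × √(1.5 × 0.75 × 0.25/53) = 14.3 points. At p = 0.5 it is 16.5. The stated 15 is reproduced to rounding, although the plan does not give p. This figure concerns the overall proportion and says nothing about predictors.

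**Non-adopters with data (derived, not stated).**

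| Reading of the plan | Arithmetic | Non-adopters |
|---|---|---|
| 48 of 59 enrol, 90% give data | (59 − 48) × 0.9 | about 10 |
| 75% uptake, 90% give data | 59 × 0.9 × 0.25 | about 13 |
| Frame enlarged to reach 48 at 75% | 48/0.75 = 64; 64 − 48 = 16; × 0.9 | 14 to 16 |
| All missing data come from opt-outs | 53 − 48 | about 5 |

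The enlarged frame matters because 75% of 59 is 44, below 48, which triggers the approach to other systems.

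**Candidates (assumption).** Four EBPAS domains, four ILS subscales, one ICS score and about five demographic items make about 14. Non-adopters per candidate: 10/14 = 0.7 to 13/14 = 0.9, and 16/14 = 1.1 at most.

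**Chance findings when nothing is real.** For k independent tests at the plan's two-sided 0.05 level, the probability of at least one is 1 − 0.95^k: 14% for k = 3, 23% for 5, 46% for 12 and 51% for 14. Simulated maximum-likelihood logistic fits with noise predictors agree:

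- 12 predictors, 10 to 13 non-adopters: about 43-50% of runs show at least one p<0.05.
- 12 predictors, 1,100 non-adopters among 5,300 practices: 48%. This rate therefore comes from the number of tests and not from the small sample.
- Three predictors: about 12%. With a Firth fit, roughly 7%.
- Backward elimination with correlated predictors and 10 to 13 non-adopters: 18-19% for 5 candidates, 37-38% for 10 and 49-53% for 15.

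**Size of a false finding.** This does depend on the number of non-adopters. For one normally distributed predictor, the log odds ratio per SD is approximately the standardised difference d, and SE(d) = √(1/a + 1/b). With 10 against 48, SE = √(1/10 + 1/48) = 0.348, so p<0.05 needs |d| above 1.96 × 0.348 = 0.68, an odds ratio of at least e^0.68 = 2.0. With 1,100 against 4,200, SE = 0.034, the threshold is 0.066, and the odds ratio need only reach 1.07.

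More predictors in the model raise the SE and so the threshold. In the simulations with 12 noise predictors and 10 to 13 non-adopters, the largest significant false odds ratio (direction ignored) had a median of about 4 to 5 per SD. With 1,100 non-adopters it was 1.08.

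**Model failure.** With 15 candidates, the full model separated or did not converge in 24% of runs with 10 non-adopters, 6% with 13 and 89% with 5.

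**Power for real effects.** The smallest univariable difference detectable with 80% power is (1.96 + 0.84) × √(1/a + 1/b): 0.97 SD for 10 against 48 and 0.89 SD for 13 against 40. With the 1.5 inflation these become 1.19 and 1.10 SD.

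**The case against.** A fair defence has four parts.

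1. **The false-finding rate is multiplicity.** This stands. A reader might infer that the shortage of non-adopters itself produces the 43-50% rate. It does not: the rate is much the same with 1,100 non-adopters. What the shortage causes is the exaggerated size of the odds ratios, the fitting failures and the low power.
2. **The number of candidates is not in the plan.** This stands too. The Aim 2 text gives two examples only. It does not say that the ILS or ICS enters this model, or that subscales enter separately, and General Considerations treats system as a random effect. A reader might infer that the plan commits to more than ten predictors and so is bound to report noise. The documents do not support that. With three to five candidates the risk is about 12 to 20%. Equally, nothing in the plan limits the number.
3. **Some apparent overfitting is irrelevant.** A model like this would also show a flattering AUC, but the plan proposes no AUC, risk score or prediction rule, so that is no criticism of it.
4. **The consequence is limited.** This is one secondary analysis in a mixed-methods aim, barriers and facilitators are also studied qualitatively, and no randomized comparison depends on it. That limits the severity. Triangulation with interviews adds context but does not correct an exaggerated odds ratio.

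The non-adopter count is also a derivation. Under the first-48 rule, some practices that are not enrolled may have been willing. Since the outcome is willingness, classing them as adopters would leave still fewer non-adopters. Uptake near 50% would ease the problem, with a smaller class of about 26, but no figure in the documents points to that.

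**Conclusion.** The concern holds in this form: the commitment to determine the most important independent predictors is not supported by the data the plan expects. On its own figures there are about 10 to 13 non-adopting practices with data, and no reading of those figures gives more than about 16.

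If the opt-out measures are all candidates, an unpenalised model is likely, though not certain, to report false or strongly exaggerated predictors. The chance of at least one is about 43-50% with 12 noise predictors, and its odds ratio is typically 4 to 5 per SD. The first figure reflects the number of tests; the second reflects the small number of non-adopters.

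The conclusion rests on the 48-of-59 target, the 75% and 90% rates, the assumed candidate list, and simulations with independent, normally distributed noise predictors. The exaggeration eases towards the upper end of the non-adopter range. A short pre-specified list removes most of the problem, so the plan should be changed, but its main comparisons are not affected.

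**What to change.** In the Aim 2 paragraph:

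- Pre-specify about two or three predictors of adoption, for example practice type, presence of behavioral health and EBPAS total score.
- Fit them with a small-sample method such as Firth-penalised logistic regression. The exact method is a matter of choice; most of the gain comes from the short list, and a significant odds ratio would still need cautious reading.
- Report all other characteristics one at a time with confidence intervals, without selection on p-values.
- Replace the sentence on determining the most important predictors with a statement that associations with adoption will be described and are exploratory.
- State how willing practices left out by the 48-practice cap will be classified.

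This changes wording only: no data, sample or procedure is affected. The cost is giving up a ranking of predictors, which the data cannot support in any case.
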